### Study Design:

#### Retrospective Quality Improvement Data

In January 2021 during COVID 19 pandemic, we launched a quality improvement project with goal to treat non-critically ill DKA patients outside of ICU setting in order to reallocate ICU beds for critically ill patients at New York Presbyterian Hospital /Columbia University Irving Medical Center. Before this quality improvement project, DKA patients were treated in the ICU setting because the DKA protocol requires hourly fingerstick glucose monitoring, which is considered higher level of care and not appropriate for stepdown unit or medical/surgical wards. During this quality improvement project, we monitored glucose levels remotely with continuous glucose monitoring (CGM) device DEXCOM G6 thus eliminating the need for hourly fingerstick glucose testing. Therefore, patients with DKA whose glucose levels have been monitored via DEXCOM G6 CGM have been treated in the stepdown unit instead of the ICU setting where glucose levels are monitoring hourly via fingerstick point of care glucose testing. We enrolled 48 patients (with additional 2 patients who had glucose levels monitored with CGM but were treated in the ICU setting therefore will not be used for this analysis).

Study participants were not being recruited and asked for their participation; non-critically ill DKA patients who presented in DKA had glucose levels monitored via CGM. Given that the recommended hourly fingerstick checks needed for treatment could not be performed on the stepdown unit and only in the ICU, the Dexcom G6 CGM device eliminated the need for hourly fingerstick checks and thus removed the barrier for patients being admitted to stepdown. Once the number of COVID cases decreased and ICU beds were more readily available, the hospital returned to practicing the pre-COVID standard of care, which was admitting DKA patient to the ICU for hourly glucose monitoring and we stopped enrolling patients for this retrospective quality improvement project

We propose to study outcomes of DKA patients who had glucose levels monitored with DEXCOM G6 CGM treated in the stepdown unit. The primary outcome is time to resolution of metabolic acidosis. Secondary outcomes are length of ICU stay, length of hospital stay, frequency of hypoglycemic episodes defined as glucose level <70 mg/dl and cost savings

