# Statistical Procedures:

The primary outcome for this study is the time to resolution of DKA. We will compare time to resolution of the DKA of patients who had glucose levels monitored via DEXCOM G6 CGM and treated in the stepdown unit (both those enrolled in the retrospective study and those who will be enrolled in the prospective study) to DKA patients who had glucose levels monitored hourly via fingerstick (and not CGM) and treated in the ICU setting.

We will perform a non-inferiority trial to study whether monitoring glucose levels via CGM in DKA patients treated in the stepdown unit is not inferior to DKA treated patients in the ICU setting with hourly fingerstick glucose monitoring.

For a noninferiority trial, based on what we have previously observed for the time to resolution of DKA, and a noninferiority margin of 1/2 the SD, we estimate that a sample size of 98 patients per group will have a 90% power to determine noninferiority at an alpha level of 0.05. Since we enrolled 48 patients in the retrospective part of the study, we will need additional 50 patients enrolled in the prospective part of the study to have 90% power and a noninferiority at an alpha level of 0.05. We plan a conservative approach where we will enroll additional 50 DKA patients who will have glucose levels monitored via CGM. We will compare with the historical control using 1:1 matching, thus will collect historical control data which include DKA patients treated for DKA in the ICU setting with hourly fingerstick glucose monitoring.

We will perform linear regression (for patients enrolled in both retrospective and prospective part of the study) to learn what clinical factors are associated with length of time to the DKA resolution. Then we will use propensity matching for historical control group (DKA patients treated in the ICU setting with glucose levels monitored via hourly fingerstick glucose levels).

To study the frequency of hypoglycemic episodes (<70 mg/dl) in patients from both prospective and retrospective study; we will use CGM glucose data stored manufacture's web based software : Clarity.

We will also evaluate frequency of hypoglycemic episodes (glucose level <70%) in historical control patients who were treated for DKA in the ICU and had hourly glucose level monitoring.

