# Study Procedures:

### Retrospective Quality Improvement Project

We will search electronic medical records (EMR) for laboratory data and clinical notes to estimate time to resolution of the DKA. Laboratory data and patient's characteristics which can contribute to time to resolution of DKA will be needed to match historical controls (DKA patients treated in the ICU setting with and glucose levels monitored via hourly fingerstick). All relevant data will be gathered from chart review and stored in Excel format on a secure Department of Surgery server. All statistical analysis will be conducted in cooperation with Center for Innovation and Outcomes Research of the Department of Surgery.

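### Does an unexplained 98 per group, with alpha 0.05 given no sidedness and no named test, make the non-inferiority conclusion unsound?

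*Combined protocol and SAP*

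**What the plan says.** The sample-size statement in Statistical Procedures reads "we estimate that a sample size of 98 patients per group will have a 90% power to determine noninferiority at an alpha level of 0.05". The margin is "a noninferiority margin of 1/2 the SD", and the calculation is said to be "based on what we have previously observed for the time to resolution of DKA". The 98 CGM patients are 48 from the retrospective project plus 50 new ones, introduced with "We plan a conservative approach where we will enroll additional 50 DKA patients". The comparator is described by "We will compare with the historical control using 1:1 matching, thus will collect historical control data".

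The section does not give the sidedness of alpha, the test or confidence limit that decides non-inferiority, the margin in hours, an assumed true difference, or any allowance for losses. The linear regression described there is for finding factors associated with time to resolution, and propensity matching is for selecting controls. Neither is a decision rule.

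**The concern.** There are two apparent problems.

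- **The number.** A margin in SD units, a power and an alpha are normally enough to fix the sample size, yet the stated values do not lead to 98. That suggests either a calculation error or an input left out.
- **The verdict.** If alpha 0.05 may be read as one-sided 0.05 (90% confidence interval) or as two-sided 0.05 (95% interval, one-sided 0.025), the same data could pass under one reading and fail under the other. The rate of falsely declaring non-inferiority at the margin would be 5% or 2.5%.

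The second problem looks sharper here because most outcomes already exist. The 48 retrospective CGM patients and 98 historical controls make 146 of 196 outcomes (74%), so a rule chosen late could be chosen by its result.

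**Working it through.** **Inputs.** From Statistical Procedures: margin 0.5 SD, power 90% (z = 1.2816), alpha 0.05, 98 per group, 1:1 matching. Assumed because not stated: zero true difference, two independent means, observed SD equal to planning SD.

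**Attempt to reproduce 98.** n per group = 2(z_a + 1.2816)² / 0.5².

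- One-sided 0.05: 2(1.645 + 1.2816)² / 0.25 = 68.5, so 69 (70 with the t distribution).
- One-sided 0.025: 2(1.960 + 1.2816)² / 0.25 = 84.06, so 85 (86 with t).

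The stated inputs alone do not give 98. A paired analysis with positive within-pair correlation needs fewer.

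**Unstated inputs that would give 98.**

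| Extra input | One-sided 0.025 | One-sided 0.05 |
|---|---|---|
| True delay allowed for | 0.037 SD | 0.082 SD |
| Inflation | 85 × 1.15 = 97.75, so 98 | 98/69 = 1.42, i.e. 42% |
| Worst-case rank-test efficiency 0.864 | 84.06/0.864 = 97.3, so 98 | 68.51/0.864 = 79.3, so 80 |

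At one-sided 0.025, three quite ordinary choices each lead to 98.

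**Power at 98.** Standard error of the difference = √(2/98) = 0.1429 SD. Power = Φ((0.5 − true delay)/0.1429 − z_a).

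| True delay | One-sided 0.05 | One-sided 0.025 |
|---|---|---|
| 0 | Φ(3.5 − 1.645) = 96.8% | Φ(3.5 − 1.960) = 93.8% |
| 0.1 SD | Φ(2.8 − 1.645) = 87.6% | Φ(2.8 − 1.960) = 80.0% |

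**Where the two readings part, unpaired.** The largest observed delay that passes is 0.5 − 1.645 × 0.1429 = 0.265 SD, or 0.5 − 1.960 × 0.1429 = 0.220 SD. The chance of landing between them is 3.0%, 7.6% and 12.0% for true delays of 0, 0.1 and 0.2 SD.

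**The same, paired.** The plan matches 1:1, so a paired analysis is plausible. At an assumed correlation of 0.3, the standard error is √(2 × 0.7/98) = 0.1195 SD. The limits become 0.5 − 1.960 × 0.1195 = 0.266 SD and 0.5 − 1.645 × 0.1195 = 0.303 SD. The whole unpaired band of 0.220 to 0.265 SD then passes under both readings. The chances of disagreement fall to 0.8%, 3.8% and 9.8%. The documents give no correlation.

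**The case for a change.** The strongest case for a change is that the primary verdict cannot be reproduced from the text. The sidedness and the test are both unstated. Combining the unpaired limits with paired limits at correlation 0.3, the observed delay at which the verdict turns could lie anywhere from 0.220 to 0.303 SD. The margin has no value in hours and its source is not named, while Study Procedures still speaks of the chart search as future work: "We will search electronic medical records (EMR) for laboratory data and clinical notes to estimate time to resolution of the DKA". With 74% of outcomes in existing records, a few sentences fixing one rule before the groups are compared would cost almost nothing and leave enrolment at 48 + 50.

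Much of this stands as a remark on reporting. The details are absent, and the analysts should settle and date them before comparing the groups. Three parts do not carry further.

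- The future chart search describes formal data abstraction. It does not show that the team had no earlier figures from a project it had already run. Those figures could also have supplied a small expected difference, which would account for 98.
- Adopting the 95% interval is not a free correction. It halves the error rate at the margin but lowers power at a true delay of 0.1 SD from about 88% to 80%. The literal wording, "will have a 90% power to determine noninferiority at an alpha level of 0.05", can fairly be read as one-sided 0.05.
- The endpoint is worded differently under Study Design ("The primary outcome is time to resolution of metabolic acidosis"). That is a separate question of definition and adds nothing to this one.

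**Conclusion.** No change to the plan follows. The figure of 98 is unexplained, but it is not shown to be wrong. It exceeds what the stated inputs require under either reading of alpha (69–70 or 85–86 per group), so there is no power shortfall on this account: about 97% or 94% against the stated 90% when there is no true difference.

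The unstated sidedness and test are a gap that an analyst would fill with a conventional choice. Either reading of alpha gives a recognised error rate and an adequately powered comparison when there is no true difference, and the choice between them is a trade-off. The readings disagree for a narrow range of results: 3.0% of the time with no true delay and 12.0% at 0.2 SD if unpaired, and less if pairing is used with positive correlation.

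This rests on zero true difference for the sample-size check, a comparison of means, observed SD equal to planning SD and, for the paired figures, an assumed correlation of 0.3. It does not address whether half an SD is a suitable margin or whether matched historical controls are comparable.

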# Remote glucose monitoring using the Dexcom G6 Continuous Glucose Monitoring (CGM) System in hospitalized patients with diabetic ketoacidosis (DKA)

Study Purpose and Rationale:

We propose to study use of Continuous Glucose Monitoring (CGM)for glucose monitoring in patients with DKA which would enable the treatment of hemodynamically stable DKA patients outside of intensive care units (ICU) thereby saving ICU beds a precious resource which have become extremely scarce resource during COVID-19 pandemic (1). In most hospitals, protocols for treatment of patients with diabetic ketoacidosis (DKA) require capillary point of care (POC) glucose testing every 1-2 hours (2) . Often, patients need to be transferred to the intensive care units (ICU) for frequent fingerstick glucose monitoring in order to safely administer intravenous insulin to treat the DKA. During the COVID-19 pandemic, this need to transfer patients to the intensive care unit (ICU) for treatment of DKA and the requirement for nurses to enter the room every 1-2 hours has contributed to scarcity of critical care unit beds and shortage personal protective equipment (PPE) Additionally, COVID-19 patients have been prone to develop DKA which has further increased the need for ICU beds (3, 4). Therefore, methods to safely and effective treat patients with DKA outside of ICU setting represent a common and pressing need.

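### The historical control pool has no dates and no stated eligibility filter, so it admits ICU patients from the period when non-critically ill DKA patients were being directed to stepdown

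*Combined protocol and SAP*

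**What the plan says.** Statistical Procedures describes the controls by setting and monitoring method only: DKA patients treated in the ICU, monitored by hourly fingerstick and not by CGM. On how they are obtained it says "We will compare with the historical control using 1:1 matching, thus will collect historical control data", and it then calls for propensity matching. Study Procedures (Retrospective Quality Improvement Project) gives the basis for matching: "Laboratory data and patient's characteristics which can contribute to time to resolution of DKA will be needed to match historical controls".

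No section gives a first or last admission date for controls, names admission date or era as a matching variable, or says that the Inclusion and Exclusion criteria apply to controls.

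Study Design (Retrospective Quality Improvement Data) describes three periods of practice at the hospital:

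- Before the project, DKA was treated in the ICU.
- From January 2021, "we launched a quality improvement project with goal to treat non-critically ill DKA patients outside of ICU setting".
- When COVID-19 cases fell, "the hospital returned to practicing the pre-COVID standard of care, which was admitting DKA patient to the ICU for hourly glucose monitoring".

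The end of the project and the start of prospective enrolment are not dated.

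**The concern.** Being in the ICU with DKA meant something different in the middle period. Before and after the project, ICU admission was routine for DKA, so ICU patients from those periods should include many who resemble the CGM group. During the project, placement depended on whether the patient was judged non-critically ill. Those still treated in the ICU without CGM are then likely to include more patients whom the CGM group leaves out, such as those with another clinical reason for ICU admission, which is an exclusion criterion.

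The control definition admits all three periods. Matching on laboratory values and patient characteristics may not fully remove selection that acted through a bedside judgement about where to place the patient. If the selected controls take longer to resolve, CGM in stepdown looks better than it is, and in a non-inferiority comparison that is the unsafe direction.

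Timing adds to this. Control outcomes already sit in the medical record, so an undefined window leaves room to settle it after results can be seen.

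**Working it through.** **Plan's own figure.** Statistical Procedures states 98 per group, a margin of half an SD, 90% power and alpha 0.05, with sidedness not given. The standard formula with no true difference is n = 2 × ((z_alpha + z_beta) / 0.5)².

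- One-sided 0.025: 2 × ((1.960 + 1.282) / 0.5)² = 84.06, so 85 per group.
- One-sided 0.05: 2 × ((1.645 + 1.282) / 0.5)² = 68.5, so 69 per group.

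Neither gives 98. The planned number is larger than these inputs require. That is a separate matter, and I take 98 (48 retrospective + 50 prospective) as given. Because sidedness is not stated, I show both levels.

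**Standard error.** In SD units with 98 independent patients per group, SE = √(2/98) = 0.143. Positive correlation within matched pairs would make it smaller, and a given shift would then matter more.

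**Shift that favours CGM.** Suppose CGM is truly worse by exactly the margin, but control times are longer by b SD through selection or era alone. The chance of wrongly declaring non-inferiority is Φ(b/0.143 − z).

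| Assumed shift b | b/SE | One-sided 0.025 | One-sided 0.05 |
|---|---|---|---|
| 0 | 0 | 2.5% | 5% |
| 0.1 SD | 0.70 | Φ(−1.26) = 10% | Φ(−0.945) = 17% |
| 0.2 SD | 1.40 | Φ(−0.56) = 29% | Φ(−0.245) = 40% |
| 0.3 SD | 2.10 | Φ(0.14) = 56% | Φ(0.455) = 68% |

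The shift is in the mean of all 98 controls, so it equals the share of affected controls times the shift among them. For example, if 48 of the 98 controls came from the project window and were slower by 0.5 SD, the mean shift would be 0.5 × 48/98 = 0.245 SD. The false non-inferiority rate would be 40% (one-sided 0.025) or 53% (one-sided 0.05).

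**Shift against CGM.** With no true difference, power is Φ((0.5 − b)/0.143 − z), where b is now the amount by which controls resolve faster.

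- b = 0: Φ(1.54) = 93.8% at one-sided 0.025, or Φ(1.855) = 96.8% at one-sided 0.05.
- b = 0.2 SD: Φ(0.14) = 56% or Φ(0.455) = 68%.

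All values of b are my assumptions. The documents give no resolution times by period, no SD and no count of ICU patients in any period.

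**The case against.** The best defence is that a historical control naturally means a patient from before the project. Study Design presents ICU care as the earlier practice and as the pre-COVID standard. The record review also covers clinical notes as well as laboratory data. Most of the Exclusion criteria (pressors, ventilation, hypotension, low GFR, altered mental status) would normally be charted, so applying them to controls would remove many of the sicker patients in any period. This has force. It shows that part of the problem can be solved with data already to be collected, but the plan neither defines the term nor says that the criteria will be applied.

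A reader might infer four stronger things that the documents do not support:

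- **That the plan ignores ICU patients treated after the project.** It is silent on them. A definition with no dates leaves them eligible; what is missing is any provision for using them.
- **That the plan intends to use project-window controls.** It only fails to exclude them.
- **That no comparable patients were in the ICU during the project.** Study Design states a goal and a count of 48 stepdown patients. It does not say that every eligible patient was diverted, or who remained. A patient could also have lacked CGM because of a device contraindication.
- **That the bias must favour CGM.** Slower resolution in sicker controls is a reasonable inference, but nothing supports a direction for calendar period alone. The protocol says "COVID-19 patients have been prone to develop DKA" and nothing about how quickly they resolve. If COVID-19 slowed resolution, pre-COVID controls would be faster than the 48 pandemic-era CGM patients, and the bias would run against non-inferiority.

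**Conclusion.** The point holds in a limited form. The control definition has no calendar window and no stated eligibility filter, and the protocol itself describes a change in ICU placement inside the span it covers. ICU patients from the project window were probably selected as sicker, and the planned matching may not fully undo that.

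The comparison is sensitive to modest residual bias. A shift of 0.2 SD in the control mean takes the false non-inferiority rate to 29% (one-sided 0.025) or 40% (one-sided 0.05), and the same shift in the other direction costs more than a quarter of patients' worth of certainty about a true null difference: power falls from about 94% to 56% (one-sided 0.025). These figures show sensitivity and do not estimate the actual bias. They rest on the assumed shifts, a normal approximation and independent groups of 98.

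**What to change.** Amend Statistical Procedures before any control outcomes are extracted:

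1. Define the control pool as ICU-treated DKA admissions with hourly fingersticks and no CGM that meet the Inclusion and Exclusion criteria as far as the chart allows, admitted before January 2021 or after the project closed. State the closing date.
2. Keep ICU patients from the project window out of the primary comparison and use them only in a sensitivity analysis.
3. Include COVID-19 status among the matching variables.
4. Report the difference in time to resolution separately for pre-project and post-project controls, beside the pooled result.

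The text should also say whether the post-project pool continues into prospective enrolment. Ending it earlier would drop patients who decline the study, who according to Alternatives receive hourly fingersticks and may be closest in time to the 50 prospective patients.

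The work is a date and eligibility filter on the record search and two extra result lines. No new patients are needed. The downside is a smaller pool: some matches may be less close, and some CGM patients, particularly those with COVID-19, may go unmatched, leaving fewer than 98 pairs.

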#### **Prospective Study**

The prospective part of this study will involve recruiting patients in the Emergency Department and offering them the opportunity to use DEXCOM G6 CGM instead of hourly fingerstick point of care glucose testing . We will enroll additional 50 non-critically ill DKA patients who will have glucose levels monitored via DEXCOM CGM and be treated in the stepdown unit. The primary outcome is time to resolution of metabolic acidosis. Secondary outcomes are length of ICU stay, length of hospital stay, frequency of hypoglycemic episodes defined as glucose level <70 mg/dl and cost savings.

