# Inclusion Criteria:

age >18, AG>20 (normal is 5-17) with bicarbonate <19 (normal is 19-27), positive urine ketones or beta hydroxybutyrate >0.3 (normal is <0.27)

glucose level >250 mg/dl on presentation to the ED

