# Exclusion criteria:

hypotension (BP below 80/60), require pressor therapy, or have any contraindication for utilizing Dexcom CGM ,, altered mental status, lack of decision making capacity, mechanical ventilation or non-invasive ventilation, chronic kidney disease with GFR <30 including patients with hemodialysis, pregnancy, other clinical reason for admission to the intensive care unit (ICU) , are excluded from study participation

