We will evaluate potential cost savings comparing treatment of DKA patients in the stepdown unit using DEXCOM G6 CGM (both retrospective quality improvement project and prospective study vs treatment of DKA patients in the ICU setting using hourly point of care glucose testing (historical controls). We will include variables such as daily cost of ICU stay vs stepdown unit, cost of DEXCOM CGM.

We will calculate satisfaction scores from nursing surveys for the prospective part of the study.

There are no validated surveys assessing provider satisfaction as use of CGM in the inpatient setting is still a novel approach. We will use a modified CGM survey used for patient/caregivers (11)

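### The CGM patients are restricted to those without ICU-level illness, but no eligibility criteria are stated for the historical ICU controls, so the primary non-inferiority comparison can be biased

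*Combined protocol and SAP*

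**What the plan says.** **CGM group.** The Prospective Study section states: "We will enroll additional 50 non-critically ill DKA patients who will have glucose levels monitored via DEXCOM CGM". The Retrospective Quality Improvement Data section describes the 48 earlier CGM patients in the same terms. It sets aside two further CGM patients because they "were treated in the ICU setting therefore will not be used for this analysis", without saying why they were in the ICU.

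**Eligibility.** The Inclusion Criteria set thresholds for anion gap, bicarbonate and ketones, and require "glucose level >250 mg/dl on presentation to the ED". The Exclusion criteria remove hypotension, pressor use, ventilation, altered mental status and GFR below 30, and end with "other clinical reason for admission to the intensive care unit (ICU) , are excluded from study participation". Neither section names a study arm.

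**Controls.** Statistical Procedures says the investigators "thus will collect historical control data which include DKA patients treated for DKA in the ICU setting with hourly fingerstick glucose monitoring". The cost comparison in the same section uses an equivalent description: "treatment of DKA patients in the ICU setting using hourly point of care glucose testing (historical controls". Neither adds a severity or eligibility restriction.

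**Matching.** Statistical Procedures says: "We will perform linear regression (for patients enrolled in both retrospective and prospective part of the study) to learn what clinical factors are associated" with time to resolution, and then plans propensity matching of the historical group. Under Study Procedures, the retrospective section adds: "Laboratory data and patient's characteristics which can contribute to time to resolution of DKA will be needed to match historical controls". No variable is listed.

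**The concern.** The primary comparison is not randomised, and its controls are drawn from existing charts. If one group is filtered for absence of ICU-level illness and the other is defined by having been in the ICU, the groups can differ in severity before monitoring method or care setting has any effect.

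In a non-inferiority test the direction matters. Controls who resolve more slowly because they were sicker lengthen the reference time and make CGM/stepdown look better than it is. A false claim of non-inferiority is the costly error, because the stated purpose is to support treating DKA outside the ICU. Controls milder than the inclusion thresholds would push the other way and cost power. The length-of-stay, hypoglycaemia and cost comparisons use the same controls.

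**Working it through.** **1. What the text settles.** Setting the sections side by side, the restriction to patients who are not critically ill is written only for CGM patients. No sentence applies the inclusion or exclusion criteria to the controls, or expressly to the 48 retrospective CGM patients. The regression that is to identify prognostic factors is run in CGM patients. If the exclusions were applied there, states such as pressor use, ventilation or GFR below 30 do not vary in that group, so the regression cannot pick them up.

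**2. The plan's own figure.** Inputs from Statistical Procedures: margin 0.5 SD, power 90%, alpha 0.05 (sidedness not stated), 98 per group. With n = 2[(z(1-α) + z(0.90))/0.5]²:

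- one-sided 0.05: 68.5, so 69 per group;
- one-sided 0.025: 84.06, so 85 per group.

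Neither gives 98, so the plan's figure is not reproduced from its stated inputs. It is larger than needed, and this does not affect the present point. I use 98 per group and show both alpha levels.

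**3. Effect of a residual shift in the controls.** The standard error of the difference is sqrt(2/98) = 0.143 SD, with 194 degrees of freedom. Let CGM be truly worse than eligible controls by exactly 0.5 SD, and let the matched controls be slower than eligible ones by b SD. The chance of declaring non-inferiority is the upper tail of a noncentral t with noncentrality b/0.143. The values of b are assumptions.

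| b (SD) | one-sided 0.025 | one-sided 0.05 |
|---|---|---|
| 0 | 0.025 | 0.050 |
| 0.05 | 0.054 | 0.098 |
| 0.10 | 0.103 | 0.172 |
| 0.20 | 0.285 | 0.401 |

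The error doubles at b = 0.045 SD (one-sided 0.025) or 0.052 SD (one-sided 0.05).

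In the other direction, with no true difference and controls faster by 0, 0.05, 0.10 or 0.20 SD, power is 0.936, 0.880, 0.796 or 0.552 at one-sided 0.025, and 0.967, 0.932, 0.874 or 0.673 at one-sided 0.05.

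**4. How much could remain after matching.** This is a simulation on assumed inputs: 98 CGM patients; a control pool of 250; each laboratory value correlated 0.3 with time to resolution; optimal 1:1 matching on one laboratory value, or on a fitted propensity score from three independent ones; 3,000 runs per case. Ineligible controls have laboratory values shifted by 0.5 SD or 1 SD. Cells give residual bias in SD, with the share of matched controls still ineligible in brackets, for the smaller / larger laboratory shift.

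| Ineligible in pool, delay | One laboratory value | Three laboratory values |
|---|---|---|
| 20%, +1 SD | 0.162 (19%) / 0.122 (17%) | 0.099 (18%) / 0.011 (13%) |
| 10%, +1 SD | 0.083 (10%) / 0.064 (9%) | 0.049 (9%) / 0.008 (7%) |
| 20%, +0.5 SD | 0.065 (19%) / 0.034 (17%) | 0.008 (18%) / -0.057 (13%) |

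The Monte Carlo standard error of each bias is at most 0.004 SD. A pool of 150 or 500 changes the bias in the 20%, +1 SD case by at most about 0.01 SD.

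False non-inferiority simulated directly for the 20%, +1 SD case, with an unpaired t-test (conservative after matching) at one-sided 0.025, is 0.180 / 0.106 with one laboratory value and 0.068 / 0.015 with three. With three laboratory values and a pool restricted to eligible controls first, it is 0.012.

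**The case against.** Four points deserve weight.

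- **Scope.** The eligibility sections are free-standing and could be read as covering everyone. But their wording concerns participation, and items such as a contraindication to the device fit people being enrolled rather than charts being pulled. This makes the scope ambiguous and leaves the gap open. The same ambiguity touches the 48 retrospective CGM patients.
- **Why past patients were in the ICU.** The protocol says DKA was treated there because of the hourly fingerstick requirement, so many controls may be comparable. That limits the likely size of the bias. It does not remove patients from the same pool who had an independent ICU indication.
- **Matching may do more than the simulation allows.** The plan promises laboratory data and patient characteristics, and chart review could capture some excluded states. That stands: the simulated shares of ineligible controls follow from the chosen inputs and do not describe this trial. Good matching can remove or overcorrect the bias. But the plan names no variable, so nothing ensures this.
- **The largest error rates are extreme.** The 29% and 40% figures need a residual of 0.20 SD, and the largest simulated residual is 0.162 SD. That stands too. The direct rates of 1.5% to 18% are the better guide to what matching leaves, and they come from the most adverse of the simulated scenarios.

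**Conclusion.** The concern holds. That the plan states no eligibility screen for the controls follows from the text alone and needs no numerical assumption. The size and direction of any bias cannot be derived from the documents; every share, delay and matching variable above is assumed. Under those assumptions the residual after matching runs from about -0.06 to 0.16 SD, while about 0.05 SD is enough to double the false non-inferiority rate. Matching on laboratory values does not itself enforce eligibility. Because this concerns the primary comparison and can be settled before control outcomes are abstracted, it should be corrected. Confidence is medium, since the effect in practice depends on who is in the ICU pool and what is matched.

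**What to change.** 1. In Statistical Procedures, require historical controls to meet the inclusion criteria and the clinical exclusion criteria at ED presentation, including absence of another clinical reason for ICU admission. Apply this before matching and without sight of outcomes. The items on device contraindication and decision-making capacity concern device use and consent and need not be carried over; state that this leaves a small difference between the groups. Confirm the same criteria for the 48 retrospective CGM patients. Repeat the primary analysis without patients whose eligibility the chart cannot settle.
2. Build the propensity model on a prespecified list of presentation variables available in both groups (for example age, glucose, anion gap, bicarbonate, renal function), fixed before control outcomes are abstracted. The CGM-only regression can stay as a descriptive analysis. Report control exclusions by reason, standardised differences after matching, and unmatched patients.

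**Cost.** Changes to protocol and SAP wording. The eligible pool will be smaller, so more charts must be screened to reach 98 matches, and some criteria, such as another reason for ICU admission, may be hard to establish from old records. No new patients are needed.
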